#### **6.4.2. Subject Discontinuation/Withdrawal from Study**

Subjects have the right to withdraw from participation in the study at any time and any reason without prejudice to their future medical care by the investigator or at the institution. If a subject withdraws from the trial, they will no longer receive treatment or be followed at scheduled protocol visits.

A subject will be withdrawn from the study for any of the following reasons:

- Subject does not meet study eligibility criteria (“screen failure”)
- Withdrawal of consent by subject or subject’s legally acceptable representative
- Lost to follow up
- Death

When a subject withdraws before completing the study, the reason for withdrawal is to be documented in the eCRF and in the source document.

#### **Withdrawal of Consent**

If the reason for withdrawal from the study is withdrawal of consent, then no additional assessments are allowed unless the Subject agrees to take part in the end of treatment visit. Subject also has the option to partially withdraw from active participation in the study and scheduled visits, but may allow status followup via telephone or medical record review.

#### **Lost to Follow-up**

A subject will be considered lost to follow-up if he or she repeatedly fails to return for scheduled visits and is unable to be contacted by the study site. A subject cannot be deemed lost to follow-

up until all reasonable efforts made by the study site personnel to contact the Subject are deemed futile.

- The study site personnel must attempt to contact the subject to reschedule the missed visit as soon as possible, to counsel the subject on the importance of maintaining the assigned visit schedule, and to ascertain whether the subject wishes to continue in the study.
- Before a subject is deemed lost to follow-up, the Investigator or designee must make every reasonable effort to regain contact with the subject (where possible, 3 telephone calls, emails, fax, and if necessary, a certified letter to the subject's last known mailing address). These contact attempts should be documented in the subject's source document.
- Should the subject continue to be unreachable despite every reasonable effort to regain contact by the site, they will be considered lost to follow-up and withdrawn from the study.

#### 6.4.3. Study Termination

The Sponsor reserves the right to terminate the study at any time for any reason. If this decision is made, all subjects will be required to be discontinued from treatment and complete the end of treatment study visit.

#### 6.5. Study Treatment Beyond Progression

Immunotherapeutic agents may produce antitumor effects by potentiating endogenous cancer-specific immune responses. The response patterns seen with such an approach may extend beyond the typical time course of responses seen with cytotoxic agents and can manifest as a clinical response after an initial increase in tumor burden or even the appearance of new lesions.

At the investigator's discretion, a participant may continue on study intervention beyond radiological progression as defined by RECIST 1.1 if the clinical condition of the participant is stable or the participant is improving symptomatically, and the investigator expects continued clinical benefit for the participant until subsequent progression determined by iRECIST criteria ([Appendix A – Assessment of Disease](#)).

In participants who have initial evidence of radiological PD by RECIST 1.1, it will be at the discretion of the investigator whether or not to continue a participant on study treatment until repeat imaging is obtained to determine whether participant's disease is progressing or the initial evidence represents a 'pseudoprogression or tumor flare'. This clinical judgment decision should be based on the participant's overall clinical condition, including performance status, clinical symptoms, and laboratory data. Participants may continue to receive study treatment until tumor assessment is repeated  $\geq 4$  weeks later in order to confirm PD by iRECIST.

Per iRECIST ([Appendix A – Assessment of Disease](#)) disease progression should be confirmed by the site in 4 to 8 weeks after site-assessed first radiologic evidence of PD in clinically stable participants. Participants who have unconfirmed disease progression may continue on treatment at the discretion of the investigator until progression is confirmed by the site, provided they have met the clinically stable definition as [Appendix A – Assessment of Disease](#), including. absence of

symptoms and signs indicating clinically significant progression of disease. Subjects should remain on the study and continue to be monitored according to the Schedule of Assessments.

Any participant deemed clinically unstable should be discontinued from study treatment at site-assessed first radiologic evidence of PD, and is not required to have repeat tumor imaging for confirmation of PD by iRECIST.

If repeat imaging does not confirm PD per iRECIST, as assessed by the investigator, and the participant continues to be clinically stable, study treatment may continue and follow the regular imaging schedule.

If PD is confirmed, participants will be discontinued from study treatment. If a participant has iCPD as defined in Appendix A, study treatment should be discontinued; however, if the participant is achieving a clinically meaningful benefit, an exception to continue study treatment may be considered following consultation with the Sponsor. In this case, if study treatment is continued, tumor imaging should continue to be performed following the intervals as outlined in [Table 6](#).

## **6.6. Duration of Follow-Up and End of Study**

The active study will end when the last subject completes the 90-day Safety Follow-up visit, approximately 2 years after enrollment.

End of treatment (EOT) visit should be performed within approximately 7 days after disease progression determination, treatment discontinuation, or immediately before initiation of any other cancer therapy, whichever is earlier.

Safety Follow-up visit should be performed 30 ( $\pm$  7) days and 90 ( $\pm$  7) days after the last administration of either agent.

Subjects who complete all 35 cycles of treatment or permanently discontinue study treatment for reasons other than objective disease progression confirmed by RECIST 1.1 and iRECIST should continue to have RECIST scans performed every 9 weeks ( $\pm$  7 days), at the investigative site or locally, up to one year after discontinuation of study treatment. Standard of care disease assessments will be collected until the start of a new anticancer treatment, disease progression, pregnancy, death, withdrawal of consent or end of study, whichever occurs first.

After disease progression or start of new anticancer treatment, subjects will be followed for survival every 90 days ( $\pm$  7 days) until death, lost to follow-up, withdrawal of consent or end of the study, whichever occurs first. Survival follow-up can be done either by in-person visit or by telephone assessment.

Subjects removed from study for unacceptable AE(s) will be followed until resolution or stabilization of the AE; in addition, the subjects will be followed for disease status and overall survival, as described above.

## 7. Study Procedures and Assessments

### 7.1. Informed Consent

A copy of the signed and dated ICF will be provided to the subject. The original ICF will be retained by the Investigator. Informed consent must be obtained prior to performing any study-specific procedures.

For subjects who wish to continue on study treatment beyond confirmed iRECIST-defined PD, a second ICF, if applicable, will be provided to the subject.

### 7.2. Study Procedures

**Schedule of Assessments** shows all procedures to be conducted at the screening visit, on-treatment, end of treatment, and follow-up visits. Refer to Section [7.4](#).

Whenever vital signs, 12-lead ECGs, and blood draws are scheduled for the same nominal time, the blood draws should occur last. The timing of the first 2 assessments should be such that it allows the blood draw (e.g., PK blood sample) to occur at the proper nominal time.

All immediate safety concerns must be discussed with the Sponsor immediately upon occurrence or awareness to determine if the subject should continue or discontinue treatment.

### 7.3. NT-I7 Pharmacokinetics

PK samples will be collected from all Phase 1b and Phase 2a subjects. Serial samples will be assessed following the PK timepoints in [Table 3](#).

*Note: The precise NT-I7 administration time and the precise PK draw time should be recorded accurately and prospectively to fully interpret these values.*

**Table 3: Pharmacokinetic Timepoints (All Subjects in Phase 1b and Phase 2a, and Biomarker Cohort)**

Treatment Cycle/Visit	Cycle 1				Cycle 2	Cycle 3		Cycle 4	Cycle 5	Subsequent Cycles (Repeat up to 2 years)	End of Tx
	Day 1		Day 2	Day 8 ± 2 days		Day 1 ± 3 days	Day 8 ± 3 days				
Scheduling Window											
Hours	0 h	2 h (±15mins)	6 h (±30mins)	24 h (±1h)							
Pharmacokinetics* (Phase 1b) & Biomarker Cohort	X a	X b	X b	X b	X	X a	X a	X	X a		X
Pharmacokinetics* (Phase 2a)	X a	X b	X b		X		X a	X		X a	X a

aTo be collected prior to study agent(s) administration on a dosing day.  
bBlood draws are timed after NT-17 administration is complete, not completion of pembrolizumab infusion.  
\*Details on blood collection, handling, and shipping are provided in the *NT-17 Laboratory Manual*.

## 7.4. Schedule of Assessments

Phase 1b and 2a															
Treatment (Tx) Cycle/ Visit	Screening	Cycle 1		Cycle 2		Cycle 3		Cycle 4	Cycle 5	Cycle 6		Subsequent Cycles (Repeat up to 2 years)	End of Tx 	Post Tx Follow U	
		Scheduling Window	Within 28 days	Day 1	Day 2	Day 8 ±2 days	Day 1 ±3 days			Day 1 ±3 days	Day 8 ±3 days			Safety FU 	Survival FU 
Pembrolizumab 		X			X			X		X	X		X		
NT-I7 		X						X			X		Odd Cycles		
Administrative Procedures															
Informed consent 	X														
Demographics	X														
Medical history	X														
Prior and concomitant medications 	X	X		X	X			X	X	X	X		X	X	X
Clinic Procedures/Assessments #															
Physical exam 	X	X			X			X		X	X		X	X	X
Performance Status 	X	X		X	X			X	X	X	X		X	X	X
Vital signs 	X	X		X	X			X	X	X	X		X	X	X
Height 	X														
Weight	X	X			X			X		X	X		X	X	X
Adverse events review 	X	X	X 	X	X			X	X	X	X		X	X	X
12-lead EKG 	X	X								X			X	X	
Cardiac enzymes (Troponin (TnI or	X	X								X			X	X	

Phase 1b and 2a															Post Tx Follow U		
Treatment (Tx) Cycle/ Visit	Screening	Cycle 1			Cycle 2			Cycle 3		Cycle 4	Cycle 5	Cycle 6		Subsequent Cycles (Repeat up to 2 years)	End of Tx 	Post Tx Follow U	
		Day 1	Day 2	Day 8 ±2 days	Day 1 ±3 days	Day 8 ±2 days	Day 15 ±7 days	Day 1 ±3 days	Day 8 ±3 days	Day 1 ±3 days	Day 15 ±7 days	Day 1 ±3 days	Day 1 ±3 days	30 days after last dose ±7 days	90 days after last dose ±7 days	Survival FU 	
Scheduling Window	Within 28 days	Day 1	Day 2	Day 8 ±2 days	Day 1 ±3 days	Day 8 ±2 days	Day 15 ±7 days	Day 1 ±3 days	Day 8 ±3 days	Day 1 ±3 days	Day 15 ±7 days	Day 1 ±3 days	Day 1 ±3 days	30 days after last dose ±7 days	90 days after last dose ±7 days	Every 90 days after last dose ±7 days	
TnT] and CK-MB) 																	
Echocardiogram 	X	X									X			X	X		
Cardiologist visit 	X	X									X			X	X		
CBC w/diff, platelets 	X	X		X	X	X 		X	X	X	X			X	X	X	
Serum chemistry 	X	X		X	X	X 		X	X	X	X			X	X	X	
PT/INR and aPTT	X	X													X		
Thyroid Function 	X	X						X			X			Odd cycles	X		
Serum or Urine Pregnancy Test 	X	X						X			X				X	X	
Urine Analysis 	X	X			X			X		X	X			X	X		
Efficacy Measurements																	
Tumor evaluation (CT/MRI) 	X				X									RECIST 1.1 and iRECIST algorithm: Every 6 weeks (± 1 week) starting at Cycle 2, Day 1 for the first 6 months, then every 9 weeks (± 1 week) until disease progression or study discontinuation.	X		
Tumor Biopsies/Archival Tissue Collection																	
Tumor Biopsy	X 						X 						X 				
Correlative Studies #																	
Immunogenicity 		X			X			X			X		Every 4 cycles 	X		X	

Phase 1b and 2a															Post Tx Follow U			
Treatment (Tx) Cycle/ Visit	Screening	Cycle 1			Cycle 2			Cycle 3		Cycle 4	Cycle 5	Cycle 6		Subsequent Cycles (Repeat up to 2 years)	End of Tx 	Safety FU 		Survival FU 
		Day 1	Day 2	Day 8 ±2 days	Day 1 ±3 days	Day 8 ±2 days	Day 15 ±7 days	Day 1 ±3 days	Day 8 ±3 days	Day 1 ±3 days	Day 1 ±3 days	Day 15 ±7 days	Day 1 ±3 days			30 days after last dose ±7 days	90 days after last dose ±7 days	Every 90 days after last dose ±7 days
Scheduling Window	Within 28 days	Day 1	Day 2	Day 8 ±2 days	Day 1 ±3 days	Day 8 ±2 days	Day 15 ±7 days	Day 1 ±3 days	Day 8 ±3 days	Day 1 ±3 days	Day 1 ±3 days	Day 15 ±7 days	Day 1 ±3 days			30 days after last dose ±7 days	90 days after last dose ±7 days	Every 90 days after last dose ±7 days
Pharmacokinetics 	Refer to Table 3 for PK sampling																	
Immunophenotyping 		X		X	X	X 		X	X	X			X 		X			
Cytokines		X		X		X 		X	X	X			X 		X			
TCR-Seq Analysis		X 					X 						X 					

#Unless otherwise specified, all clinic procedures and sample collection are to be done prior to NT-I7 and/or pembrolizumab dosing. More details in the *NT-I7 Laboratory Manual*.

Pembrolizumab should be administered on Day 1 of each three-week cycle after all procedures/assessments have been completed.

NT-I7: Dose as assigned; once every 6 weeks, starting Cycle 1, Day 1. NT-I7 should be dosed after pembrolizumab on concurrent treatment days.

Written consent must be obtained prior to performing any protocol specified procedure.

Prior medications – Record all medications (prescription and over-the-counter [OTC]) taken within 30 days of Screening visit. Concomitant medications – Enter all medications (prescription and OTC) taken between 7 days prior to Cycle 1, Day 1 through the Safety Follow-up visit.

Full physical exam is required during Screening, Day 1 of every cycle, End of Treatment, and Safety Follow-up visits. A directed physical exam may be performed on other days as clinically indicated.

Performance status must be assessed per ECOG Performance Scale criteria.

Vitals (blood pressure, heart rate, respiratory rate, temperature) to be collected in a standardized manner in a sitting position after the subject has rested comfortably for ~5 minutes. On the odd-numbered cycles (pembrolizumab and NT-I7), vitals need to be obtained within 60 minutes prior to the start of the pembrolizumab infusion AND repeated after the completion of the pembrolizumab infusion, but before the NT-I7 injection. On the even-numbered cycles (pembrolizumab only), vitals need to be obtained within 60 minutes prior to the start of the pembrolizumab infusion.

Height is measured on the first visit during Screening only.

All AEs, including those meeting serious criteria, from the time of consent through the 30-day safety follow-up visit, and AEs meeting serious criteria only from 30 days following cessation of study treatment to 90-day safety follow-up visit. See Section 11 for additional details on reporting of AEs.

Duplicate EKG, at least 5 minutes apart, and serum cardiac enzyme levels (Troponin (TnI or TnT) and CK-MB) must be obtained at Screening, C1D1, every 4 cycles (i.e., C5D1, C9D1,..), and End of Treatment. A patient should be assessed by a PI or a local cardiologist to determine if the EKG and the serum cardiac enzyme levels are clinically significant. If either is found to be clinically significant, see footnote 30.

Hematology includes complete blood count (CBC) with differential, including but not limited to red blood cell (RBC) count, hemoglobin, hematocrit, white blood cell (WBC) count with differential (neutrophil count including lymphocyte, monocyte, eosinophil, basophil counts and bands), absolute neutrophil count (ANC), and platelet count.

Chemistry includes (but is not limited to) sodium, potassium, calcium, phosphorus, chloride, magnesium, bicarbonate, blood urea nitrogen (BUN) or urea, serum creatinine, glucose, uric acid, albumin, total protein, alkaline phosphatase, lactate dehydrogenase, bilirubin (indirect and direct), aspartate serum glutamic oxaloacetic transaminase (AST/SGOT), alanine aminotransferase/serum pyruvic transaminase (ALT/SGPT).

Thyroid function testing: thyroid-stimulating hormone (TSH), free triiodothyronine (T3) (or total T3 for sites where free T3 is not performed), and free thyroxine (also known as free T4)

Serum pregnancy test to be performed at the Screening visit for all females except those surgically sterile or 2 years postmenopausal. Subsequent serum or urine pregnancy tests could be performed as noted or per Investigator's discretion. If the serum screening pregnancy test is performed > 72 hours before first dose, a serum or urine pregnancy test should be repeated prior to dosing.

Urinalysis (a urine dipstick may be used) at Screening and D1 of each cycle.

Baseline CT/MRI tumor imaging must be performed within 28 days prior to first dose for all subjects. Scans performed as part of routine clinical management are acceptable for use as the baseline scan if they are of diagnostic quality and performed within the allotted screening window. The exact same image acquisition and processing parameters should be used throughout the study. The first on-study imaging time point will be performed 6 weeks ( $\pm$  1 week) or earlier if clinically indicated, regardless of any treatment delays, for up to 6 months, and every 9 weeks ( $\pm$  1 week) thereafter. Brain and/or bone lesions may be scanned if applicable. (Note: Subjects do not need to undergo the next scheduled tumor imaging if it is less than 4 weeks after the previous scan.) See Section 13 and [Appendix A – Assessment of Disease](#) for further information.

Biopsy will be performed during screening for those subjects who did not have enough archival tumor tissue and are required to have pre-treatment tumor biopsy per protocol.

Samples for immunogenicity assays shall be collected pre-dose from all study subjects in Phase 1b, Biomarker Cohort, and in up to 10 subjects in each of the arms of Phase 2a. Samples shall be collected pre-dose on C1D1, C2D1, C3D1, and C5D1. Thereafter, samples shall be collected pre-dose on every 4 cycle such as C9D1, C13D1, C17D1, C21D1, and so on. Testing may be conducted as indicated above, and repeated at 90-day follow up visit, if positive at the end of treatment visit.

For sampling details of PK, please refer to [Table 3](#). Additional information on handling and shipping are provided in the *NT-I7 Laboratory Manual*.

Whole blood will be collected for the multispectral immunophenotyping to obtain absolute cell counts for CD4+ and CD8+ T-cell subsets and activation states, NK cells, B cells, and other cell types as necessary.

TCR-seq analysis will be performed on both whole blood (pre- and on-treatment) for all Phase 1b and selected Phase 2a arms - TNBC (Arm I), MSS-CRC (Arm IV and Arm IVa), PC (Arm V and Arm Va), and the Biomarker Cohort (only for subjects who have dose of NT-I7 increase to 1200  $\mu$ g/kg at C5D1). TCR-seq whole blood sample should be taken pre-dose at C1D1 visit. On-treatment whole blood sample should be taken at the same visit (pre- or post-biopsy) as on-treatment tumor biopsy collection (C2D15 $\pm$ 7 days).

End of Treatment visit will occur approximately anytime within 7 days after disease progression determination or treatment discontinuation.

Safety follow-up visits will be performed in clinic visit will be performed every 30 days and 90 days after last dose of treatment.

Optional tumor biopsy at Cycle 6, Day 15 ( $\pm$  7 days) only for CPI naïve R/R OC Biomarker Cohort (only for subjects who have dose of NT-I7 increase to 1200  $\mu$ g/kg at C5D1), CPI-naïve R/R MSS-CRC Arm IVa, and CPI-naïve R/R PC Arm Va.

Applicable only for CPI naïve R/R OC Biomarker Cohort (only for subjects who have dose of NT-I7 increase to 1200  $\mu$ g/kg at C5D1), CPI-naïve R/R MSS-CRC Arm IVa, and CPI-naïve R/R PC Arm Va.

Optional visit applicable only for the CPI naïve R/R MSS-CRC Arm IVa and CPI-naïve R/R PC Arm Va expansion cohorts.

Visit must be performed in person during Phase 1b for PK sampling and may be performed in clinic or by telephone during Phase 2a.

Survival follow-up by telephone will be performed every 90 days starting 90 days after Safety follow-up day 90 until death, lost to follow up, withdrawal of consent, or end of study, whichever occurs first, to find out the survival status, new anti-cancer treatments and the outcome of any ongoing adverse event(s).

For all Phase 1b dose-escalation and selected Phase 2a arms - TNBC (Arm I), MSS-CRC (Arm IV and Arm IVa), PC (Arm V and Arm Va), and Biomarker Cohort, mandatory biopsies are required pre- and on-treatment. On treatment biopsies will be taken at C2D15 ( $\pm$  7 days). If C3D1 (C2D15 + 7 days) is decided for the biopsy, the biopsy has to be taken before dosing on Cycle 3.

If either the EKG or serum cardiac enzyme levels are clinically significant, an echocardiogram must be performed and the patient must be assessed by a local cardiologist to rule out the potential presence of myocarditis and to ensure there are no clinically significant abnormalities in the echocardiogram before enrolling in or continuing treatment. The next dosing will be suspended during the follow-up period until confirmation is obtained through an echocardiogram.

CONFIDENTIAL

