The Biomarker Cohort will enroll up to 10 evaluable subjects with CPI-naïve R/R Ovarian Cancer (OC). The starting dose level of NT-I7 is planned at 960 µg/kg IM Q6W to further evaluate the tolerability of the starting regimen. Pembrolizumab dose is fixed at 200 mg IV Q3W. Subjects who tolerate at least 4 cycles of treatment without Grade  $\geq 3$  AEs and all Grade 2 AEs have resolved to Grade  $\leq 1$ , the dose may be escalated to NT-I7 1200 µg/kg IM Q6W at Cycle 5. This cohort will test intra-patient dose escalation and collect samples for biomarker analyses at 2 different dosages.

One treatment cycle is defined as 21 days (3 weeks) with NT-I7 administered intramuscularly (IM) once every 6 weeks (Q6W), and pembrolizumab administered intravenously (IV) once

every 3 weeks (Q3W). On days where both drugs are given, pembrolizumab will be given prior to NT-I7. Completion of 35 cycles of administration (approximately 2 years) with pembrolizumab and NT-I7.

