## 5.7. Study Schema

## 5.8. Treatment Schema

Radiological tumor assessments will be conducted every 2 cycles (6 weeks  $\pm$ 1 week) during the first 6 months, and every 3 cycles (9 weeks  $\pm$ 1 week) thereafter. Confirmatory scans must be performed at >4 weeks after initial assessment of response to confirm a best response of CR or PR, whenever disease progression is suspected (e.g., symptomatic deterioration), and at End of Treatment visit. If disease progression is identified by RECIST 1.1, a second scan will be scheduled 4-8 weeks later to confirm disease progression by iRECIST. (See Section 13 and Appendix A for details).

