### 13.2. Tumor Imaging During the Study

The first on-study imaging assessment should be performed at 6 weeks ( $\pm 1$  week) from the date of the first study treatment. Subsequent tumor imaging should be performed every 6 weeks ( $\pm 1$  week) or more frequently if clinically indicated. After the first 6 months, subjects who remain on treatment will have imaging performed every 9 weeks ( $\pm 1$  week). Imaging timing should follow calendar days and should not be adjusted for delays in cycle start dates. Imaging should continue to be performed until disease progression is identified by the investigator, or notification by the Sponsor, whichever occurs first.

Brain MRI is required during the study only if:

- The screening brain scan is positive (has tumor lesion)
- The subject develops sign/symptoms suggestive of brain metastasis

Brain CT imaging is acceptable if MRI is medically contraindicated or cannot be scheduled in a timely manner.

Objective response should be confirmed by a repeat imaging assessment. Tumor imaging to confirm PR or CR should be performed at least 4 weeks after the first indication of a response is observed. Subjects will then return to regular scheduled imaging, starting with the next scheduled imaging time point. Subjects who receive additional imaging for confirmation do not need to undergo the next scheduled tumor imaging if it is less than 4 weeks later; tumor imaging may resume at the subsequent scheduled imaging time point.

Per iRECIST ([Appendix A – Assessment of Disease](#)) disease progression should be confirmed by the site, 4 to 8 weeks after site-assessed first radiologic evidence of PD in clinically stable subjects. Subjects, who have unconfirmed disease progression may continue on treatment at the discretion of the investigator until progression is confirmed by the site, provided they have met the conditions detailed in [Appendix A – Assessment of Disease](#). Subjects who receive confirmatory imaging do not need to undergo the next scheduled tumor imaging if it is less than 4 weeks later; tumor imaging may resume at the subsequent scheduled imaging time point, if clinically stable. Subjects, who have confirmed disease progression by iRECIST, as assessed by the site, will discontinue study treatment. Exceptions are detailed in [Appendix A – Assessment of Disease, Table 6](#).

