4.9.2.1 Best Overall Response per RECIST 1.1

The derivation rules of confirmed response in table 3 are listed for RECIST 1.1.

Table 3 Derivation of Confirmation of Response from Timepoint Overall Response

Response at First Time Point	Response at Subsequent Time Point	BOR with Confirmation per RECIST 1.1
CR	CR	CR
CR	PR	SD, PD, or PR ^a
CR	SD or PD	SD provided minimum criteria ^b for SD duration met, otherwise PD
CR	NE	SD provided minimum criteria ^b for SD duration met, otherwise NE
PR	CR or PR	PR
PR	SD	SD
PR	PD	SD provided minimum criteria ^b for SD duration met, otherwise PD
PR	NE	SD provided minimum criteria ^b for SD duration met, otherwise NE

BOR = best overall response; CR = complete response; PR = partial response; SD = stable disease, PD = progressive disease; NE = not evaluable.

^a If a CR is truly met at first time point, then any disease seen at a subsequent time point, even disease meeting PR criteria relative to baseline, makes the disease PD at that point (since disease must have reappeared after CR). Best response would depend on whether minimum duration for SD was met. However, sometimes ‘CR’ may be claimed when subsequent scans suggest small lesions were likely still present and in fact the subject had PR, not CR at the first time point. Under these circumstances, the original CR should be changed to PR and the best confirmed response is PR.

^b Minimum criteria for SD duration is 4 weeks.

A BOR of CR or PR must be confirmed by a tumor assessment that should be performed no less than 4 weeks after the criteria for response are first met. One intervening response SD is allowed for PR confirmation (PR SD PR=PR; PR SD CR=PR if confirmed CR is not achieved).

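### The Schedule of Assessments starts tumour imaging at week 3 but footnote 16, Section 13.2 and the SAP start it at week 6; under the 4-week rule for stable disease the choice can change a subject's SD/PD status

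*Protocol*

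**What the plan says.** Four places give a start for on-study imaging.

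- **Protocol 7.4, tumour evaluation row:** a mark in the Cycle 2 Day 1 column, and 6-weekly imaging "starting at Cycle 2, Day 1 for the first 6 months".
- **Protocol 7.4, footnote 16, attached to that row:** "The first on-study imaging time point will be performed 6 weeks" (±1 week), or sooner where there is a clinical reason.
- **Protocol 13.2:** "The first on-study imaging assessment should be performed at 6 weeks" (±1 week), counted from first study treatment.
- **SAP 4.9.1:** the same first-scan time as Section 13.2.

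Protocol 5.1 fixes the cycle length: "One treatment cycle is defined as 21 days (3 weeks"). Section 5.8 gives the interval, "Radiological tumor assessments will be conducted every 2 cycles (6 weeks"), but no separate start. Section 13.2 adds: "Imaging timing should follow calendar days and should not be adjusted for delays in cycle start dates". Footnote 16 also has a skip rule: "Subjects do not need to undergo the next scheduled tumor imaging if it is less than 4 weeks after the previous scan".

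For best overall response, SAP 4.9.2.1 states: "Minimum criteria for SD duration is 4 weeks". SAP 4.9.4.2 applies the same 4 weeks to DCR, from first dose to the last assessment that is neither PD nor not evaluable.

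**The concern.** The Schedule row and its own footnote cannot both be followed as routine. A site that works from the row scans at weeks 3, 9, 15 and 21. A site that works from the footnote or Section 13.2 scans at weeks 6, 12, 18 and 24. Imaging is tied to calendar days, so the two sequences never converge.

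Progression is dated at a scan, so the schedule affects observed PFS. It also affects DCR through the 4-week rule, since stable disease at week 3 does not qualify and stable disease at week 6 does. Two further points depend on it:

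- **Evaluability.** The efficacy evaluable set (SAP 3.3) needs one evaluable post-baseline tumour assessment. A week-3 scan can bring in subjects who leave between weeks 3 and 6.
- **DMC review.** Protocol 15.4 ties the interim review of each Simon arm to the first tumour assessment of the 17th evaluable subject. That falls at week 3 or week 6, depending on the text followed.

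**Working it through.** **Calendar check.** Inputs: 21-day cycle (Protocol 5.1), 6-week interval and ±1-week window (Protocol 5.8, 13.2).

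- The plan's own interval reproduces: 2 × 21 / 7 = 6 weeks.
- Cycle 2 Day 1 is study day 21 + 1 = 22, which is week 3. Six weeks is study day 42 + 1 = 43, which is Cycle 3 Day 1.
- With ±7 days the windows are days 15–29 and 36–50. They do not overlap, so visit tolerance cannot absorb the conflict.
- Grid A (Schedule row): weeks 3, 9, 15, 21, 30… Grid B (footnote 16, 13.2, SAP): weeks 6, 12, 18, 24, 33… They stay 3 weeks apart after the change to 9-weekly scans.

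**Stable disease.** This step needs no model beyond on-time scans.

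| Progression occurs | Grid A | Grid B | Same status? |
|---|---|---|---|
| before week 3 | PD at week 3 | PD at week 6 | yes |
| weeks 3–6 | SD at week 3 (under 4 weeks), PD at week 9: PD | PD at week 6 | yes |
| weeks 6–9 | SD at week 3 (under 4 weeks), PD at week 9: PD | SD at week 6 (qualifies): SD | **no** |
| after week 9 | SD at week 9 qualifies | SD at week 6 qualifies | yes |

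Under the ±3-day visit window the latest Cycle 2 Day 1 scan is day 25, which is 24 days after first dose and short of 28. Only a scan at the far end of a ±7-day window (day 29, 28 days after first dose) would just reach 4 weeks.

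**Size, under an assumption.** The documents give no PFS assumption. I take an exponential time to progression with true median m weeks, S(t) = 2^(−t/m), on-time scans, and every subject on one grid.

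- DCR: A = S(9), B = S(6).
- 3-month PFS (13 weeks): the last scan is week 9 on A and week 12 on B, so A = S(9), B = S(12).
- Observed median: the first scan at which S(t) ≤ 0.5.

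Worked line for m = 9: S(6) = 2^(−6/9) = 63.0%, S(9) = 2^(−1) = 50.0%, S(12) = 2^(−12/9) = 39.7%.

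| True median (weeks) | Observed median, A vs B (weeks) | 3-month PFS, A vs B (%) | DCR, A vs B (%) | DCR gap (points) | Gap in 25 subjects |
|---|---|---|---|---|---|
| 6 | 9 vs 6 | 35.4 vs 25.0 | 35.4 vs 50.0 | 14.6 | 3.7 |
| 9 | 9 vs 12 | 50.0 vs 39.7 | 50.0 vs 63.0 | 13.0 | 3.2 |
| 12 | 15 vs 12 | 59.5 vs 50.0 | 59.5 vs 70.7 | 11.3 | 2.8 |
| 18 | 21 vs 18 | 70.7 vs 63.0 | 70.7 vs 79.4 | 8.7 | 2.2 |
| 26 | 30 vs 33 | 78.7 vs 72.6 | 78.7 vs 85.2 | 6.6 | 1.6 |

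Gaps are taken from unrounded values. The 3-month PFS gap runs from 10.4 points (35.4 − 25.0) down to 6.1 (78.7 − 72.6).

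**Simon design.** An exact search for 4% vs 21% at one-sided 0.025 and 80% power returns 0/17 and 3/25 (alpha 0.0164, power 0.8001), which matches the planned 17 + 8 = 25. Scan timing does not enter this calculation.

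**The case against.** The strongest reply is that three of the four places agree, that footnote 16 sits on the very row at issue and sends the reader to Section 13, and that nothing in the documents shows any site scanning at week 3. The endpoints that move most are secondary and descriptive, with no comparison planned. With 25 subjects an exact 95% interval around 40% runs from about 21% to 61%, wider than any shift above. PFS also counts deaths, and scans are allowed when progression is suspected, so a model with events seen only at scheduled scans overstates the effect.

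Most of this stands, and it limits the size of the point. It does not remove the contradiction. The allowance for an earlier scan is for an individual clinical reason and does not cover a routine scan for everyone. The skip rule does not help either: week 6 is 3 weeks after week 3, so a site that scans at week 3 may drop the week-6 scan.

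A reader might infer more than the documents support:

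- **That PFS is biased in one direction.** The observed median moves by 3 weeks, but either way: 9 vs 6 at a true median of 6 weeks, 9 vs 12 at a true median of 9.
- **That real events would be censored as following missed assessments.** SAP Table 4 requires two or more consecutive missed assessments. Both grids are spaced 6 weeks apart, so a subject scanned on time on either one has no such gap. An effect here is speculative.
- **That the primary endpoint is compromised.** A CR or PR needs confirmation at least 4 weeks later, so confirmed ORR is little affected apart from the evaluability effect. That effect is itself limited, because Section 13.3 asks for a scan at treatment discontinuation.

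**Conclusion.** The contradiction is real, current and exactly 3 weeks in size. It is more than clerical, because the SAP's own 4-week rule gives a subject who progresses between weeks 6 and 9 a different SD/PD status on each schedule. That conclusion rests only on the documents and on-time scans.

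The percentages rest on more: an exponential curve, true medians of 6 to 26 weeks, and all subjects on one grid compared with all on the other. Under those assumptions DCR differs by about 7 to 15 points (roughly 2 to 4 subjects in 25) and 3-month PFS by about 6 to 10 points. Mixed use across sites gives smaller differences. Who is efficacy evaluable and when the DMC review falls due can also change. The documents do not show which schedule sites followed, and this point does not say which first-scan time is right.

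**What to change.** Reconcile the Section 7.4 row and its Cycle 2 Day 1 mark with footnote 16, Section 13.2 and SAP 4.9.1, so that all four give one first-scan time.

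For scans already taken at about week 3, keep the actual scan dates in the analysis. Re-labelling scans to a nominal grid by calendar date would not help: week 9 is equidistant from weeks 6 and 12 and outside both ±1-week windows (weeks 5–7 and 11–13), and PFS uses the date of progression in any case.

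Add a DCR sensitivity analysis to the SAP that reports how many subjects' SD/PD status depends on the schedule they followed. There are two groups: those whose only non-PD scan fell before 4 weeks and who had PD at about week 9, and those whose SD rests on a single scan at about week 6 with PD at the next. Recounting the first group as SD, and separately the second as PD, brackets the effect.

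The cost is one table row in the next amendment or a clarification letter to sites, plus a short SAP paragraph. It needs no new data and no change to the sample size.
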